The aim of this study is to determine whether the use of a liposomal bupivacaine based periarticular injection versus a ropivacaine based periarticular injection improves pain control in patients undergoing Total Hip and Knee arthroplasty at Kootenai Health. We intend to evaluate pain control by using a Pain Score measured every four hours during hospitalization.

Primary Outcome Variable

Pain Scores as averaged over length of stay. The Pain Scale routinely used at Kootenai Health will be utilized. This is the standard 0-10 scale with 0 being no pain to 10 which is the worst possible pain the patient has experienced.

Secondary Outcome Variable

Narcotic consumption (calculated in oral morphine equivalent dose)

Length of Stay (hours)

Setting/Resources for the Study

Kootenai Health will be the setting for the surgeries while [name] clinic will be the setting for subject recruitment. Subjects will be screened and enrolled by [name]. Surgery will be performed by [name]. Other surgeons may join the study but all will be performing the same injection technique. [name] will oversee the training of the surgeons and any other key research personnel that may join the study.

Study Design

This study will employ a prospective, randomized, double-blind, study design methodology.

Study Subjects

All subjects who have been routinely referred to [name] for total hip or knee arthroplasty will be screened for inclusion into this study.

Inclusion Criteria

- 30 - 85 years of age
- Hip or knee Arthritis (osteoarthritis, post traumatic, inflammatory, and avascular necrosis)

Exclusion Criteria

- Multiple daily doses of long acting Narcotics (such as Oxycontin, MS Contin, or Fentanyl patches etc.)
- Revision surgery
- Surgical complication (femoral fracture with implant insertion)
- Inability to provide Informed Consent

Subject Recruitment/Screening/Consent

Patients will be screened and consented during a routine pre-operative office visit to discuss their pending surgery. This will take place in a private consultation room to ensure privacy. It will be made very clear to patients that their participation is voluntary and that choosing not to participate in the study will in no way affect their future care by [name] or Kootenai Health.

Study Procedures

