Total Hip and Knee arthroplasty is a standard procedure at Kootenai Health and routinely performed by the principal investigator. Patients will be randomized to either a ropivacaine based periarticular injection or a liposomal bupivacaine based periarticular injection (See Table 1).

Table 1. Periarticular Injection Assignments

Group A	Group B
20 mL Liposomal Bupivacaine	
25 mL Bupivacaine 0.5%	49.25 mL 5mg/ml Ropivacaine
1.0 mL 1:1000 Epinephrine	1.0 mL 1:1000 Epinephrine
0.8 mL Clonidine 100 mcg/mL	0.8 mL Clonidine 100 mcg/mL
13.7 mL NaCl 0.9%	13.7 mL NaCl 0.9%
1.0 mL Ketorolac (15 – 30 mg)*	1.0 mL Ketorolac (15 – 30 mg)*

*May be deleted for patients with compromised renal function

The randomization schedule will be set up using a routine alternating treatment assignment between each patient in a 1:1 pattern using an excel spreadsheet. The group assignment will be written on an order sheet and will be taken to the pharmacy where the pharmacist will mix the injection according to standard of care and as noted in Table 1. The Investigator will not be blinded to the treatment but the post-operative providers will be blinded to the randomized assignment group. An Advanced Registered Nurse Practitioner who routinely rounds on post-operative patients to evaluate their pain control will be blinded to the assignment group.

Early Withdrawal of Subjects

A patient may be withdrawn from the study prior to the expected completion of that subject for failure to adhere to protocol requirements, or subject consent withdrawal or the investigator may withdraw the patient for safety concerns. Patients may choose to withdraw from the study at any time. Data that have already been collected prior to consent withdrawal will still be used.

Statistical Plan

This is a non-inferiority trial. Therefore, the main output from the analysis above will be a 95% confidence interval for the difference between average pain scores for the hospitalization. It is anticipated that 118 130 patients will be enrolled into each cohort with an enrollment period of 3 years. A biostatistician will be consulting on the study and performing statistical calculations. Mean pain scores will be compared between the two groups within each cohort. Opioid use (morphine equivalents) will be compared from PACU admission to discharge. Length of stay, calculated in hours from the start of the surgical procedure until time of discharge, will be compared between the two groups within each cohort.

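### The aim is one question about hip and knee patients, but the pain-score comparison is defined only within each cohort, with no overall estimate and no rule if the cohorts disagree.

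*Combined protocol and SAP*

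**What the plan says.** The Primary Objective has a single aim: whether the liposomal bupivacaine injection, against the ropivacaine one, "improves pain control in patients undergoing Total Hip and Knee arthroplasty at Kootenai Health". There is no separate hip or knee objective. The Primary Outcome Variable is "Pain Scores as averaged over length of stay", on a 0-10 scale.

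The Statistical Plan opens with "This is a non-inferiority trial" and continues that "the main output from the analysis above will be a 95% confidence interval for the difference between average pain scores for the hospitalization". No analysis is described above that sentence, and the sentence does not say which patients the interval covers. Enrolment is set by cohort: "It is anticipated that 118 130 patients will be enrolled into each cohort with an enrollment period of 3 years". The pain comparison follows: "Mean pain scores will be compared between the two groups within each cohort". Length of stay is handled in the same way. The opioid sentence carries no cohort limit: "Opioid use (morphine equivalents) will be compared from PACU admission to discharge".

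The word cohort is never defined. Because the two treatment groups sit inside each cohort, a hip cohort and a knee cohort is the natural reading, and I use it below. Study Procedures describes one alternating 1:1 allocation list with no mention of joint. The Data and Safety Monitoring Plan speaks of one sample at the halfway look and one study to stop.

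**The concern.** The aim, the allocation list and the interim look treat this as one study of both joints. The pain analysis as described gives two results, one per joint. There is no pooled or joint-stratified estimate, no arm-by-joint comparison, and no statement of whether both cohorts, or either, must show non-inferiority.

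Two things are at stake. First, if one cohort's interval excludes the margin and the other's does not, the conclusion on the stated aim would be chosen after seeing the data. Second, a question about all patients would be answered with intervals that each use only about half of them.

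**Working it through.** **Inputs.** From the Statistical Plan: 118 or 130 patients per cohort (both figures stand in the text), so 59 or 65 per arm with 1:1 allocation; non-inferiority; 95% CI, hence one-sided 0.025. Assumed because the documents do not state them: SD, margin, no true difference, two cohorts of equal size, and the same SD and effect in both joints.

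**1. The plan's own sample size.** It cannot be reproduced, since margin, SD and power are absent. Solving backwards, margin/SD = (1.96 + z_power) × √(2/n).
- 80% power: 2.80 × √(2/65) = 0.49, or 2.80 × √(2/59) = 0.52.
- 90% power: 3.24 × √(2/65) = 0.57, or 3.24 × √(2/59) = 0.60.

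**2. Precision.** Half-width = t × SD × √(2/n per arm). At SD 2:
- one cohort, 65 per arm: 1.98 × 2 × √(2/65) = 0.69 points;
- both cohorts, 130 per arm, adjusted for joint: 1.97 × 2 × √(2/130) = 0.49 points.

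Apart from the small change in t, the ratio is √2 = 1.41 whatever the SD. Each cohort CI is about 41% wider than the overall one; equivalently, the overall one is about 29% narrower.

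**3. Split verdicts at SD 2, margin 1.** Let p be the power in one cohort (noncentral t, noncentrality = margin / [SD × √(2/n)]). The cohorts are independent, so both succeed with probability p² and exactly one with 2p(1 − p).
- 65 per arm: noncentrality 1/0.351 = 2.85 and p = 0.808. Both: 0.65. Exactly one: 2 × 0.808 × 0.192 = 0.31. Overall estimate (130 per arm): 0.980.
- 59 per arm: p = 0.768. Both: 0.59. Exactly one: 0.36. Overall: 0.969.

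**4. Varying both unstated inputs.** Chance of a split verdict at 65 per arm, with the power of the overall estimate in brackets:

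| SD | margin 0.5 | margin 1 | margin 1.5 |
|---|---|---|---|
| 1.5 | 50% (76%) | 7% (>99%) | about 0% (>99%) |
| 2 | 41% (52%) | 31% (98%) | 2% (>99%) |
| 2.5 | 32% (36%) | 47% (89%) | 14% (>99%) |

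With equal effects, 2p(1 − p) cannot exceed 50%, which it reaches at p = 0.5.

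**5. What an overall estimate does not do.**
- Discordance remains. At SD 2, margin 1 and 65 per arm, the overall CI shows non-inferiority while at least one cohort CI does not in about a third of trials: 98.0% − 65.2% = 32.8%, since the overall result practically always succeeds when both cohorts do.
- Claims multiply. If either cohort could claim success alone, the chance of at least one false claim with both true differences at the margin is 1 − 0.975² = 4.9%. Adding an unordered overall claim raises it to about 5.8% (simulation).
- The interaction is imprecise. Its half-width is 1.97 × 2 × √(4/65) = 0.98 points at SD 2, about the size of the assumed margin.

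**The case against.** The strongest reply is that separate answers may be what the sponsor wants. Enrolment is set per cohort, and the Background says that a randomized knee study exists while hips had not been studied in this way. On that view hip and knee verdicts may differ without leaving a question open, and no precision is lost. This stands as a reason to keep the within-cohort comparisons. It does not supply a result for the aim as written, or a rule for reading two results against it.

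Four stronger readings are tempting, and the documents do not support them.
- *The plan promises one interval covering both joints and then contradicts itself.* The sentence promises "a 95% confidence interval for the difference between average pain scores for the hospitalization" and names no population; it could mean one interval per cohort. The fault is an unspecified population.
- *Every analysis is by cohort.* This holds for pain score and length of stay, but the opioid sentence has no such limit.
- *Split verdicts are likely.* The chance runs from about 0% to 50% over the inputs tried. Without a margin, a non-inferiority verdict is not even defined.
- *Half the precision is thrown away.* A cohort has half the information (1/variance), but in interval width the factor is 1.41, and it is a loss only for the overall question.

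It is also fair to object that a bare overall estimate would add a third claim without removing discordance. That is correct, and it is why the fix needs an order of claims.

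**Conclusion.** The point holds as a gap in specification. The stated aim spans both joints, the pain comparison is defined only by cohort, and there is no overall estimate and no rule for disagreement. This rests on reading cohort as hip or knee.

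The gain in precision is firm given equal cohorts with a common SD and effect: an overall CI about 29% narrower than either cohort CI. The split-verdict figure is not firm. The 31% belongs to one assumed combination (SD 2, margin 1, 65 per arm, no true difference) and shows only that the risk can be material. The change is worth making, but it does not show that the planned cohort comparisons are wrong.

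**What to change.** In the Statistical Plan:
1. Define cohort, and keep the within-cohort comparisons as planned.
2. Add one overall estimate of the arm difference in average pain score, from a model with arm and joint (hip or knee) fitted to all patients. Name its 95% CI as the answer to the combined aim.
3. Report the arm-by-joint interaction with its CI as descriptive, given a half-width of about 1 point at SD 2.
4. Prespecify that the overall CI is read first, and that joint-specific claims then rest on the cohort CIs in a fixed, named order. State that an overall result does not by itself support a claim for a joint whose own CI is inconclusive.

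None of these verdicts can be reached until the non-inferiority margin is stated, so it must be given as well.

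The cost is a few sentences and one extra model, with no new patients or data. The downside is that the overall estimate averages over any true hip-knee difference, which the interaction has limited precision to detect; the retained cohort results remain the place to look for it.

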Confidentiality and Management and protection of Data

Information about study subjects will be kept confidential and managed according to the Health Insurance Portability and Accountability Act of 1996 (HIPAA).

Patient data will be entered into electronic spreadsheets and paper data forms. One spreadsheet, enrollment form, will contain the patient name, medical record number, study number and randomization group. The second spreadsheet will contain the study number, patient demographic and study data. Only the investigators will have access to the files and their passwords. Data will be stored on the Kootenai Health protected and secured main computer system. Any paper records will be stored in hard copy in a locked filing cabinet in the investigator's office for a minimum of five years. At this time the information will be destroyed in accordance with the Kootenai Health document destruction policy. An electronic database such as REDCap may be used for data storage and will have password protected, limited access.

Results and Publication Plan

The data from this study will be shared at Kootenai Health. External dissemination of the results in journal publication is under consideration. All data will be aggregated and de-identified.

Medical Care and Compensation for Injury

If patients are injured from taking part in this research study, medical care will be provided. The costs of the care will be billed to the patient or his/her insurance. No funds have been set aside to pay the patient in the event of a research related injury. Study participants will be instructed to contact the investigator for more information.

References

3. Schroer, W. A prospective randomized periarticular trial of liposomal bupivacaine. Paper #2. Presented at: American Association of Hip and Knee Surgeons Annual Meeting; Nov. 7-9, 2014; Dallas.

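### No baseline covariate is prespecified for the pain or opioid comparison; adjusting within each cohort for age and recorded pre-operative opioid use would buy some precision cheaply

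*Combined protocol and SAP*

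**What the plan says.** The combined protocol and SAP describes the analysis in one paragraph, under Statistical Plan. It declares "This is a non-inferiority trial" and states that "the main output from the analysis above will be a 95% confidence interval for the difference between average pain scores for the hospitalization". The pain comparison itself is one sentence: "Mean pain scores will be compared between the two groups within each cohort". Opioid use, in morphine equivalents from PACU admission to discharge, is also compared, but that sentence does not say by cohort. Length of stay is compared by cohort. No regression model, covariate or stratification factor is named for any of the three. The paragraph points back to an analysis above it that does not appear in the document.

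The baseline information is described elsewhere:

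- **Age:** Inclusion Criteria, 30 to 85 years.
- **Opioid history:** Exclusion Criteria, which bar patients on "Multiple daily doses of long acting Narcotics". No other level of opioid use is excluded, and none is said to be recorded.
- **Pain scale:** Primary Outcome Variable says "The Pain Scale routinely used at Kootenai Health will be utilized", a 0-10 scale. No pre-operative score is listed.
- **Study file:** the confidentiality section says "The second spreadsheet will contain the study number, patient demographic and study data", without listing the items.

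**The concern.** The conclusion depends on whether a confidence limit clears a margin, so the width of the interval matters directly. Part of the patient-to-patient variation in mean pain and in opioid totals can plausibly be predicted before surgery. Age spans 55 years. Prior opioid use is a plausible predictor of both outcomes, and users of short-acting opioids, or of less than the excluded regimen, remain eligible. A comparison of means without covariates leaves all of that variation in the standard error.

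Leaving the model unstated has a second cost. If covariates are brought in later, they may be chosen after the data have been seen. Naming them in advance removes that possibility, and it also guards against chance imbalance in opioid users between arms.

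**Working it through.** **The plan's own figure.** The only figure is the enrolment: "It is anticipated that 118 130 patients will be enrolled into each cohort". Two numbers stand side by side, and no margin, SD, power or dropout rate is given, so the sample size cannot be reproduced. With 1:1 allocation, 118 or 130 per cohort means 59 or 65 per arm. Solving backwards at one-sided 0.025, (1.960 + 0.842) × √(2/n) gives a standardized margin of 0.516 (n = 59) or 0.491 (n = 65) for 80% power. These are back-calculations and not inputs from the documents.

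**Inputs.**

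- Per arm: n = 65, from reading the cohort as 130 split 1:1.
- SD of mean in-hospital pain: 2 points (assumed; 1.5 and 2.5 also tried).
- r, the correlation of the covariates jointly with mean pain within arm: 0.2, 0.3 or 0.5 (assumed).
- Margin, for power only: 1 point (assumed), with a true difference of zero.

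**Formulas.** Residual SD = SD × √(1 − r²). Half-width = t × residual SD × √(2/n), with t = 1.979 on 128 degrees of freedom. The equivalent increase in sample size is 1/(1 − r²) − 1.

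**Unadjusted.** √(2/65) = 0.1754, and 1.979 × 2 × 0.1754 = 0.694.

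| r | Variance removed | Residual SD | Half-width | Power at 1 point | Equivalent extra patients |
|---|---|---|---|---|---|
| 0 | 0% | 2.000 | 0.694 | 80.8% | none |
| 0.2 | 4% | 1.960 | 0.680 | 82.3% | 4.2% |
| 0.3 | 9% | 1.908 | 0.662 | 84.3% | 9.9% |
| 0.5 | 25% | 1.732 | 0.601 | 90.4% | 33.3% |

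Three covariates use three of the 128 degrees of freedom, which leaves t at 1.979 to three decimals. Fitting weak covariates therefore costs almost nothing.

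**Sensitivity to the other assumptions** (r = 0.3, 1-point margin):

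| SD | Per arm | Power unadjusted | Power adjusted |
|---|---|---|---|
| 1.5 | 65 | 96.5% | 97.7% |
| 2 | 59 | 76.8% | 80.6% |
| 2.5 | 65 | 61.9% | 66.0% |

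The proportional narrowing, 1 − √(1 − r²), depends on r alone: 2.0%, 4.6% and 13.4% for r = 0.2, 0.3 and 0.5. Whether it changes the chance of success depends on the SD and the margin, which are not stated.

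**Joint.** Within a cohort of a single joint, joint explains none of the variance. If hips and knees were pooled half and half, a hip-knee difference of 1 point at SD 2 would explain (1²/4)/(2² + 1²/4) = 0.25/4.25 = 5.9%, and a difference of 0.5 points would explain 0.0625/4.0625 = 1.5%. This is relevant only to the opioid sentence, which carries no cohort qualifier.

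**The case against.** The strongest reply is that this is a preference about efficiency whose size rests on assumed inputs. That largely stands. SD, margin and correlation are absent from the documents, and the number per arm depends on how the enrolment figure is read. At r = 0.2 the gain is 0.014 points of half-width. Nothing in the documents shows that age plus a yes/no opioid flag would reach 0.3 to 0.5, particularly once one group of heavy users has been excluded. No figure can be given for the opioid outcome.

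A reader might also infer more than the documents support, in four ways:

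- **That joint is ignored.** Pain is compared within each cohort. Cohort is not defined, but the treatment arms are called groups and patients are enrolled into each cohort, so hip and knee is the natural reading. Joint is then already handled for pain.
- **That the covariates are already in hand.** Only age clearly is. Opioid history must be asked, but the documents do not say that use short of the exclusion is recorded, and no pre-operative pain score is mentioned.
- **That raw means were a deliberate choice.** The plan does not use the word unadjusted and gives no reason for or against adjustment. It is silent.
- **That the comparison is invalid without covariates.** Leaving out covariates does not in itself bias a randomized comparison. The allocation here is a "routine alternating treatment assignment between each patient in a 1:1 pattern", so imbalance need not be due to chance alone. That is a separate matter, and adjusting for measured factors would protect against it only in part.

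**Conclusion.** The point holds as a low-cost improvement. No covariate adjustment is specified for pain or for opioid use, although age is available and opioid history has to be asked at screening. Under SD 2 and 65 per arm, adjustment narrows the 95% interval for pain from ±0.69 to between ±0.68 and ±0.60 for r from 0.2 to 0.5. The lower end is slight and the upper end is worth having. With r near zero nothing material is gained, and almost nothing is lost. The benefit for morphine equivalents is plausible but cannot be quantified from the documents. The missing margin and SD are a separate gap.

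**What to change.** In the Statistical Plan, define cohort (hip, knee) and prespecify the following, before the interim analysis planned at 50% accrual:

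1. **Pain:** within each cohort, an ANCOVA of mean in-hospital pain on treatment, age, pre-operative opioid use (yes/no, recorded at the screening visit) and, if recorded, one 0-10 pain score from that visit. The 95% interval for the adjusted treatment difference becomes the main output.
2. **Morphine equivalents:** adjust for age and pre-operative opioid use, and state that this analysis is also done by cohort.
3. **Sensitivity:** report the unadjusted differences for both outcomes.

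The cost is a change of model and one or two data fields at a visit that already takes place, with no extra visit and no new instrument. The new fields may be missing for patients already enrolled, so the plan should say how missing covariate values are handled. If the pain score would be missing for many patients, it can be left out and the model kept to age and opioid use.

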Protocol

A Prospective, Randomized Clinical Trial of Two Periarticular Multimodal Drug Injections in Total Hip and Knee Arthroplasty

Principal Investigator

[name] MD

Version Date

June 9, 2016

Background

Perioperative pain control is a fundamental part of patient satisfaction. Many therapies are aimed at improving this critical component during a hospitalization. Current pain management techniques use several different mechanisms simultaneously and are termed "multi-modal". Multi-modal therapy has demonstrated improvement in pain control after surgery while minimizing side effects. Advancement in the understanding and practice of multimodal pain management is one of the prime reasons for shorter hospital stays.

A key component of the multimodal approach to pain management is the intra-operative surgical site injection of a local anesthetic or drug cocktail. There are many formulations used for this purpose. A formulation documented in the literature was implemented by this institution which has dropped the average length of stay dramatically. Concern over the limited half-life of the administered anesthetic and the continued need for opioid administration has led to a search for better drug formulations and administration vehicles. Recently, the FDA approval of an extended release bupivacaine called liposomal bupivacaine was thought to extend the effective half-life of the anesthetic agent and thereby prolong post-operative anesthesia. Use of liposomal bupivacaine in total joint surgery was almost universally adopted after its recent approval and has been an integral part of the "same day total joint" movement.

Upon the approval of liposomal bupivacaine by the FDA, there have been a number of studies examining the efficacy of the drug in the orthopedic patient population. Liposomal bupivacaine is expensive and adds to the burden of procedural cost. Studies, often conflicted by industry sponsorship, have suggested improvement in pain control and shortened hospitalizations with the use of liposomal bupivacaine. Other studies have raised questions about the effectiveness of this agent. Recently a randomized double blind study was performed with total knees which demonstrated no improvement in pain management with the addition of liposomal bupivacaine to the multimodal pain management protocol. This study has not been performed in the hip arthroplasty population.

Primary Objective:

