The formulation of liposomal bupivacaine allows for a longer duration of action and a slower absorption into systemic circulation, avoiding high plasma concentrations. Local infiltration can result in significant system plasma concentrations for up to 96 hours; however, significant levels are not correlated with local efficacy and differ between surgical procedures. Because of the longer lasting plasma concentrations there is concern for potential drug interactions should another local anesthetic be used during this 96-hour time period. Kootenai Health recently instituted a procedure placing a colored armband on every patient receiving liposomal bupivacaine and providing written information about the drug including time the drug was given and when the 96-hour time period is over. Patients are blinded to their treatment assignment and to maintain the blind, all study patients will receive the armband and information. This will provide the same standard of care to participants randomized to the liposomal bupivacaine group and will not incur risk to those randomized to the ropivacaine group. This information will be included in the consent form.

Breach of confidentiality is a risk of this study in the transfer of data for research purposes.

Reporting of Serious Adverse Events

Reports of unanticipated adverse events will be submitted to the IRB upon discovery following the correct policies and procedures. Copies of each report and documentation of IRB notification and receipt will be kept in the Investigator's records.

Data and Safety Monitoring Plan

Because both groups are receiving well established standard of care treatment, the Principal Investigator will oversee the safety of the study. This safety monitoring plan will include careful assessment and appropriate reporting of adverse events as noted above. Ongoing evaluation of subject eligibility, adverse events, and the informed consent process will occur with compliant reporting to the IRB of protocol deviations. The Principal Investigator will closely monitor for

trends in the data or a higher than expected rate of occurrence for any adverse effect such as a higher than expected use of pain medication in either group.

In addition, a blind interim analysis of the data will be conducted by the statistician when 50% of the sample is accrued. If the results show statistically overwhelming significant differences between groups, the blind will be broken and the study stopped.

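### Does the 50% interim look need a written boundary, outcome and cohort rule before its stopping rule is acceptable?

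*Combined protocol and SAP*

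**What the plan says.** The Data and Safety Monitoring Plan states that "a blind interim analysis of the data will be conducted by the statistician when 50% of the sample is accrued", and then: "If the results show statistically overwhelming significant differences between groups, the blind will be broken and the study stopped". That is the whole rule. The preceding paragraph of the same section gives the Principal Investigator ongoing oversight of adverse effects, "such as a higher than expected use of pain medication in either group".

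Other sections bear on how the rule would be read:

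- Primary Outcome Variable names a single outcome, the 0-10 pain score averaged over the stay. Narcotic consumption and length of stay are secondary.
- Statistical Plan calls the trial non-inferiority and says "the main output from the analysis above will be a 95% confidence interval for the difference between average pain scores for the hospitalization".
- Statistical Plan also says "Mean pain scores will be compared between the two groups within each cohort".
- On size it says "It is anticipated that 118 130 patients will be enrolled into each cohort with an enrollment period of 3 years". Two figures are printed side by side, so both are used below.
- Background says of the earlier randomized knee study: "This study has not been performed in the hip arthroplasty population".

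No margin, standard deviation, power or effect size is given.

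**The concern.** A rule that can end the whole study would normally state what is tested, at what level and in which patients. Here all three are left to interpretation.

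The obvious worry is that hip and knee are analysed separately but stopped together. A striking result in one joint could cut the other short at about half its planned size. If the knee cohort triggered the stop, the loss would fall on the hip population, which Background singles out as unstudied. A look at unspecified data could also be read as letting a secondary outcome trigger the stop. And an unwritten rule can be interpreted after the interim results are known.

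**Working it through.** The plan prints no interim figure to reproduce, so the check asks how much each reading would change.

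**Inputs.** From the protocol: 118 or 130 per cohort (read as cohort totals), 1:1 allocation, a look at 50%, a final 95% interval. Assumed: SD 2 (range 1.5-2.5), boundary two-sided p<0.001 (|z|>3.291), even accrual in the two cohorts, normal approximation.

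**Type I error.** The interim and final z statistics have correlation √0.5. Total two-sided error is 1 − P(|Z₁|<c, |Z₂|<1.960):

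- look at p<0.001: 5.02%
- look at p<0.01: 5.5%
- look at p<0.05: 8.3%

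At p<0.001, the chance of a false stop with no true effect is 0.1% for one comparison, 0.2% for two cohorts, and 0.6% for two cohorts and three outcomes if these are independent.

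For non-inferiority, a false early claim would need a crossing in favour of the tested arm while the truth lies on the unfavourable side. That has probability below 0.001/2 = 0.05%.

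**Chance of stopping.** SE = 2·SD/√n. At the look one cohort has n = 59, so SE = 4/√59 = 0.521. Pooled, n = 118 and SE = 4/√118 = 0.368. With a true difference d in one cohort and none in the other, the z mean is d/0.521 by cohort and (d/2)/0.368 pooled. If P is the crossing probability in the affected cohort, the either-cohort rule stops with probability 1 − (1 − P)(0.999).

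| True difference, one cohort only | Either cohort | Pooled |
|---|---|---|
| 0 | 0.2% | 0.1% |
| 0.5 | 1.1% | 0.5% |
| 0.75 | 3.3% | 1.2% |
| 1.0 | 8.6% | 2.7% |
| 1.5 | 34% | 10.5% |

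Requiring both cohorts to cross gives under 0.1% in every row. Over SD 1.5-2.5 and 118-130 per cohort, the either-cohort figure at 1.5 points runs from 16% to 77%. At 1.0 point the z mean runs from 1/(5/√59) = 1.54 to 1/(3/√65) = 2.69, which gives about 4% to 27%. At 0.5 point it is about 0.7% to 2.7%. With t quantiles, the 34% becomes 29%.

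If both cohorts share a 1.0-point difference, the order reverses: pooled 28%, either 16%, both 0.7%.

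**What a halted cohort loses.** The 95% half-width goes from 1.96 × 0.368 = 0.72 to 1.96 × 0.521 = 1.02 points, a ratio of √2 = 1.41. The interval stays valid: the other cohort consists of different patients, so stopping on their data does not bias it. The chance of showing non-inferiority at a true difference of 0 is Φ(margin/SE − 1.96):

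| Assumed margin | Full cohort | Half cohort |
|---|---|---|
| 0.5 | 27% | 16% |
| 1.0 | 78% | 48% |
| 1.5 | 98% | 82% |
| 2.0 | 100% | 97% |

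The drop at margin 1.0 is close to the largest in this range.

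**Loss before knowing whether a stop occurs** (margin 1.0, either-cohort rule):

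- 1.5 points in the other cohort: 0.341 × 48.4% + 0.659 × 77.5% = 68%
- 1.0 point: 0.085 × 48.4% + 0.915 × 77.5% = 75%
- 0.5 point: 0.010 × 48.4% + 0.990 × 77.5% = 77%

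These compare with 78% (77.5%) when no stop is possible.

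**The case for a change.** The best case for a change is that the text never settles whether one cohort's crossing ends both. No default is neutral: the either-cohort rule stops more often than pooling when the effect is in one joint, and less often when both joints share it. Under Study Procedures the investigator is not blinded, and under the confidentiality section only investigators have access to the files, one of which holds the assignments. People who can see results by arm could therefore interpret an unwritten rule. Accrual may also be uneven: at an assumed 2:1 split the slower cohort would have about 39 patients at the look and an interval 1.73 times as wide as planned. Clarifying costs one paragraph.

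Much of this stands as description. The either-or-both question is open, and a sentence filed before the look would do no harm. The claim that type I error is safe holds only for a strict boundary; at p<0.05 it would not. But a p<0.05 result is not a fair reading of *overwhelming*, and the look belongs to the consulting statistician.

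The case for opioid use as a trigger is weak. The sentence on pain medication describes the Principal Investigator's adverse-effect monitoring; the statistician's look is introduced separately after it. The reversal between scenarios also counts against a required change, because it shows that no single rule is better throughout.

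**Conclusion.** The gap is one of detail that a competent statistician would fill sensibly: average pain score, compared within each cohort, at a strict level. On that reading the two-sided error is 5.02% and the final 95% interval needs no adjustment.

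The remaining choice, whether one cohort's result stops the other, is a trade-off for the sponsor. Its cost is small unless a large effect is confined to one joint. At SD 2 and 118 per cohort, the chance of an either-cohort stop is 1.1% at 0.5 point and 8.6% at 1.0 point, and it reaches 34% only at 1.5 points against exactly zero in the other cohort. Nothing in the protocol suggests such a contrast.

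The conclusion rests on the assumed p<0.001 boundary, the assumed SD and margin, even accrual, hip and knee as the cohorts, and 118 or 130 as cohort totals. A smaller SD raises the stop probabilities (to 27% at 1.0 point with SD 1.5 and 130 per cohort). No wrong result has been shown and no alternative rule is clearly superior, so the plan need not change.
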